## 9.2 Reporting

### 9.2.1 Adverse Events (AE) and Severe Adverse Events (SAE) Reporting

All serious adverse events, whether or not deemed expected or device-related, must be reported to the clinical monitor immediately or within 24 hours of knowledge by telephone (see below). A written report must follow within five (5) working days and is to include a full description of the event and sequence. If the Lumenis monitor cannot be reached, the site personnel will directly contact the Lumenis Communication Center (USA) at [contact].

If an anticipated adverse event occurs at any time during or after the use of the study device, the Investigator must report it to Lumenis. If the anticipated adverse event, in the opinion of Lumenis or the Investigator, is likely to affect the safety of the subjects or the conduct of the study, the IRB/ethic committee will be notified of the effect as required by the authorized representative.

The Investigator shall report to the EC and regulatory authorities serious adverse events and device deficiencies that could have led to a serious adverse device effect, if required by the national regulations or by the EC.

## 9.3 Risk/ Benefit Analysis

### 9.3.1 Anticipated Procedure Related Adverse Events

Anticipated adverse events that are related to the BPH Vaporization procedure performed as part of this study and as established in the literature are noted below [Error! Reference source not found.]. These complications are related to BPH Vaporization, whether or not ablation is performed, and regardless of the method that is used for either removal or the adenoma.

- Intraoperative complications: bleeding, prostate capsular perforation, infection and different risks due to the anesthesia
- Postoperative complications: Dysuria, hematuria, urge incontinence, urinary retention, urgency, infection

### 9.3.2 Anticipated Device Related Adverse Events

The potential risks related to the system may include prostate capsule perforation and bleeding. Nevertheless, this modified system is based on the previous marketed family of Ho:YAG lasers that is already largely used in the clinical arena, and for the same indications. The use of Ho:YAG for ablation of the prostate adenoma has been shown to be safe and effective with a very low rate of complications [Error! Reference source not found. Error! Reference source not found.].

Finally, the modified system underwent a thorough series of pre- clinical verification and validation testing to ascertain its maintained safety and performance as well as the safe and effective use of the Xpeda fibers.

### 9.3.3 Anticipated Benefits

**DOC No.: 1005715**

Revision: B

State: Released

ECO No: GEN-0007426

Effective Date: 02-Jun-2016

**Description: Surgical. Protocol LUM-SBU-VP-15-02, Ablation efficacy of contact side firing fiber in predefined settings for treating BPH**

The Holmium laser has been shown to be able to vaporize soft tissues and in particularly prostate adenoma diagnosed as BPH. Due to the high-energy power of the Lumenis pulse 120H and the usage of side firing fiber this tissue can be ablated quite easily. The Xpeeda fiber was design to work in full contact with the tissue thus delivering maximum energy for efficient vaporization. Bleeding control is successfully utilized with the holmium laser and the specific settings of the Lumenis pulse 120H. Using fiber defocusing or wider pulse size (predefined settings designed for the double puddle of the device) will minimize intraoperative complications. Moreover, the vaporization efficacy of the pulse 120H may lead to reduced procedure time and postoperative complications, including readmission as compared to the other commonly used parameters and devices for BPH treatment.

## **10 Administrative Procedures**

### **10.1 Investigator Selection**

The investigator must be of good standing as an investigator and knowledgeable in relevant areas of clinical research to ensure adherence to the requirements of the protocol, including the protection of human subjects. Other site personnel must have appropriate research experience and infrastructure to ensure adherence to the protocol and enrollment of sufficient numbers of evaluable subjects. The curriculum vitae (CV) of the Investigator will be maintained in the Sponsor files as documentation of previous medical training, and federal databases will be searched to ensure that the investigator and/or the site are not prohibited from engaging in federally sponsored clinical research. The Principal Investigator will sign the signature page of this protocol, agreeing to comply with all applicable government regulations and the requirements of this study.

### **10.2 IRB / Ethical Committee Approval**

This clinical study will be conducted according to all applicable regulations under the Medical Device Directive and in accordance with the ICH Good Clinical Practice and local laws and regulations relevant to the use of medical devices.

An Ethical Committee (EC or IRB) will approve the clinical study protocol prior to study initiation. Approval will be indicated in writing with reference to the final protocol number and date. Details regarding the IRB / EC's constitution including the names of its members, their qualifications and what function they perform on the board (e.g., chairman, specialist, lay-member) will be made available to enable Lumenis and the Investigator to conform to regulations governing research on experimental devices.

### **10.3 Informed Consent**

Prior to the procedure, the Investigator or his delegate must explain to each subject (or the subject's legally authorized representative) the nature of the study, its purpose, expected duration, and the benefits and risks of study participation. After this explanation and before entering the study, the subject (or legally authorized representative) must voluntarily sign and date the IRB (EC) -approved Informed Consent form.

**Description: Surgical. Protocol LUM-SBU-VP-15-02, Ablation efficacy of contact side firing fiber in predefined settings for treating BPH**

#### 10.4 Subject Withdrawal/Dropouts

The subjects will be advised in the written Informed Consent form that they have the right to withdraw from the study at any time without prejudice, and may be withdrawn at the Investigator's/Lumenis' discretion at any time. In the event that a subject drops out of the study or is withdrawn from the study, the Exit/Termination CRF should be completed. On the withdrawal page, the Investigator should record the date of the withdrawal, the person who initiated withdrawal and the reason for withdrawal.

Reasonable effort should be made to contact any subject lost to follow-up during the course of the study in order to complete assessments and retrieve any outstanding data and study supplies. The records of subjects who terminate prior to completing the study will be retained and the reason for termination will be documented.

The following are possible reasons for subject dropout/withdrawal:

- Adverse event that would prevent subject compliance with the protocol;
- Subject withdrawal of consent;

However, every effort should be made to see that subject is followed for the remainder of the study even if subject is unable or unwilling to comply with the protocol.

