## 3 Study Design

This is a one arms, prospective, single center study. Subjects will undergo a single treatment for ablation of the prostate using the study device. Follow up visits are scheduled for the day of release

**Description: Surgical. Protocol LUM-SBU-VP-15-02, Ablation efficacy of contact side firing fiber in predefined settings for treating BPH**

from the hospital and at 1 and 3 months post procedure. Additional treatment sessions, if required, will be at the discretion of the investigator, as part of the site standard of practice. Additional sessions will not be included in this study.

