## 6 Patient Population

### 6.1 Source and Sample Size

Subjects shall be selected by the physician within his patient population. One (1) site will participate in this study and will treat twenty (20) subjects. Enrolled subjects that did not complete the full course of the study will be discarded from performance analysis if they have not returned for the 1 and/or 3 month follow-up visits.

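### Section 10.4 lets the investigator or sponsor withdraw an already treated subject without any criterion, and section 6.1 then drops that subject from the performance analysis

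*Combined protocol and SAP*

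**What the plan says.** Section 10.4 (Subject Withdrawal/Dropouts) tells subjects they may leave at any time and adds that they "may be withdrawn at the Investigator's/Lumenis' discretion at any time". Its list of possible reasons for dropout or withdrawal includes "Adverse event that would prevent subject compliance with the protocol".

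The same section has safeguards. For subjects lost to follow-up, "Reasonable effort should be made to contact any subject lost to follow-up during the course of the study in order to complete assessments". On withdrawal, "the Investigator should record the date of the withdrawal, the person who initiated withdrawal and the reason for withdrawal". Also, "The records of subjects who terminate prior to completing the study will be retained and the reason for termination will be documented". It closes by asking that "every effort should be made to see that subject is followed for the remainder of the study", even where the subject cannot or will not comply.

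Two other sections matter. Section 3 (Study Design): "Subjects will undergo a single treatment for ablation of the prostate using the study device"; any further session falls outside the study. Section 6.1 (Source and Sample Size): "Enrolled subjects that did not complete the full course of the study will be discarded from performance analysis", the condition being that they did not return for the 1 and/or 3 month visit.

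**The concern.** Discretion to withdraw a subject normally serves to stop study treatment. Here treatment is complete after one procedure. What remains is discharge, the 1-month visit and the 3-month visit, so withdrawing a treated subject can only end data collection.

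The discretion can also follow outcome. In a single-arm study at one site, the surgeon knows procedure time, energy used, capsule perforation, conversion to TURP and blood loss at or around surgery. Section 8.2 adds an interim look at immediate post-operative data after at least 10 subjects, when follow-up may still be open. A man with a difficult operation or a complication could therefore leave before month 3 by someone else's decision, with no stated criterion to test that decision against.

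At stake are the 3-month efficacy results and the completeness of safety observation in a study of 20 men with no control arm.

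**Working it through.** **Step 1: follow a treated subject through the text.** The plan states no dropout rate, power, effect size or SD, and section 8.1 plans descriptive analysis only, so there is no figure of its own to reproduce.

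- Section 10.4: withdrawal by investigator or sponsor is allowed at any time. No criterion is given, and before and after treatment are not separated.
- Section 3: treatment is a single session. Withdrawal after surgery therefore ends follow-up and nothing else.
- Section 5.1.1 and Table 1: ablation rate and ablation efficacy use the pre-treatment and 3-month TRUS, and TRUS is scheduled only at baseline and 3 months. A subject withdrawn before month 3 has neither endpoint.
- Section 6.1: a non-completer who misses the 1 and/or 3 month visit leaves the performance analysis. The term is not defined. If it covers all efficacy endpoints, ablation time is lost too, although it was measured on the day of surgery.
- Section 8.1: reported adverse events are listed, and no exclusion of withdrawn subjects is stated. Events before withdrawal stay in; events afterwards may go unobserved.

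**Step 2: how large could the effect on a mean be?** Inputs: n = 20 (section 6.1). Assumptions: normally distributed endpoint, SD = 1, and k = 1, 2 or 3 subjects lost, who are exactly the worst k.

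The expected values of the three lowest of 20 standard normal observations are −1.867, −1.408 and −1.131. The expected shift in the mean is minus the sum of the lowest k, divided by (20 − k):

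- k = 1: 1.867 / 19 = 0.098 SD
- k = 2: (1.867 + 1.408) / 18 = 3.275 / 18 = 0.182 SD
- k = 3: (1.867 + 1.408 + 1.131) / 17 = 4.406 / 17 = 0.259 SD

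The standard error of the 20-subject mean is 1/√20 = 0.224 SD, so these are about 0.44, 0.81 and 1.16 standard errors. A simulation of 400,000 samples gives the same shifts, and a mean sample SD among the remaining subjects of about 0.90, 0.85 and 0.80.

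The direction is favourable: upward for ablation rate and ablation efficacy, downward for ablation time if longer is worse.

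**Step 3: imperfect selection.** The 3-month volume is not known when an early withdrawal is decided. If the decision rests on day-of-surgery information with correlation ρ to the endpoint (bivariate normal), the shift is ρ times the figure above:

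| k | perfect selection | ρ = 0.5 | ρ = 0.3 |
|---|---|---|---|
| 1 | 0.098 SD | 0.049 | 0.029 |
| 2 | 0.182 SD | 0.091 | 0.055 |
| 3 | 0.259 SD | 0.130 | 0.078 |

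Both values of ρ are assumptions.

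**Step 4: dependence on normality.** In general, losing k subjects whose mean lies d SD below the rest shifts the mean by k·d/20. One subject at d = 1 gives 0.05 SD; three at d = 2 give 0.30 SD. A heavy tail can thus exceed the normal figure for k = 3.

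**The case against.** The other side has several sound points.

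- **Nothing in 10.4 removes anyone from the results.** A reader might infer that it does. The removal comes from section 6.1 and is limited to the performance analysis. The documents do not support saying that poor safety outcomes are deleted, since section 8.1 lists reported adverse events without such an exclusion. This stands; the weakness lies in the two sections acting together.
- **The adverse-event reason is narrow.** A reader might take any adverse event as grounds to leave. The text limits it to one that prevents compliance, and the closing sentence asks that a subject unable to comply still be followed. This stands in large part. But the compliance that remains after surgery is attending visits, and a man with a serious complication may be among the likeliest to miss them.
- **10.4 does not contradict itself.** A reader might see a contradiction between the discretion and the closing sentence. That sentence reads as a qualification. What remains is a gap: it speaks of subjects unable or unwilling to comply and does not say that it governs a withdrawal chosen by the investigator or sponsor.
- **Withdrawals are already documented.** Date, initiator and reason are recorded and records are kept. That makes a withdrawal traceable but does not prevent it, and no section commits to reporting these exits.
- **The perfect-selection figures are not a forecast.** They assume the lost men are exactly the worst. Nothing in the documents links complications to a low ablation rate, and a descriptive analysis has no test or threshold for the shift to cross. This stands.

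Nothing in the documents suggests that the discretion is meant to be used selectively.

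**Conclusion.** The point holds as a weakness in the rule, worth correcting because the correction is cheap. Sections 10.4 and 6.1 together leave a route by which a treated subject can be taken out of follow-up on someone else's decision, after much of his surgical outcome is known, and then be left out of the performance results. The safety consequence is truncated observation.

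The size cannot be derived from the documents. For normal data and perfect selection, the expected shift is about 0.10, 0.18 or 0.26 SD for 1, 2 or 3 lost subjects. It falls to about 0.03 to 0.08 SD at an assumed correlation of 0.3. These figures show what the rule permits; how often it would be used is unknown.

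**What to change.** In section 10.4:

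- State that withdrawal at the investigator's or sponsor's discretion applies before treatment only, with a recorded reason, and define when treatment begins for this purpose.
- State that after treatment an individual's follow-up ends only when the subject withdraws consent. Study-wide termination under section 10.13 is unaffected.
- State that neither an adverse event nor non-compliance is a reason to end follow-up, and amend the adverse-event item in the list accordingly.
- Extend the closing sentence to all treated subjects, subject to their right to withdraw consent.

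In section 6.1, replace the discard rule so that every treated subject is accounted for:

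- Report day-of-surgery endpoints and safety for all treated subjects.
- Report 3-month endpoints for everyone with a 3-month TRUS, whether or not the 1-month visit took place.
- List each post-treatment exit with its reason, initiator and the data known at that date.

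The 6.1 change is needed as well: if only 10.4 changes, a treated subject who misses a visit is still discarded. The cost is protocol and consent-form wording, plus one listing in the report. The sponsor gives up a discretionary right over individual subjects after treatment.

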#### 10.5 Case Report Forms/Data Collection

The Investigator is responsible for completely and accurately recording study data in the appropriate sections of the CRFs provided by Lumenis. The CRFs must be signed by the Investigator or by his/her authorized person as designated in a note to file.

The monitor will ensure the quality of data recording at each investigational site by comparison to supporting source documents during periodic site visits. Adherence to proper recording of information as well as assuring that corrections are being made will also be addressed during these periodic visits.

Data will be recorded on the following CRFs. Where data is not located in the subject's source file, the CRF will be the source for this data.

#### 10.6 Required Documentation

Prior to starting the clinical study, the following documents must be submitted or returned to Lumenis by the Investigator:

- Signed Clinical Trial Acknowledgement for the protocol
- Signed Clinical Evaluation Agreement
- Curriculum vitae of the Principal Investigator
- Signed Financial Disclosure Statement for each investigator
- Written approval from the Ethical Committee of both the protocol and informed consent form

**Description: Surgical. Protocol LUM-SBU-VP-15-02, Ablation efficacy of contact side firing fiber in predefined settings for treating BPH**

## 10.7 Subject's Financial Compensation

Subjects participating in this study will not be compensated for participating in this study.

## 10.8 Device Use/Accountability

The evaluation site personnel will maintain records of the model and serial number of the device (if appropriate) used for each treatment during the conduct of the study. The device along with the associated delivery and accessories are to be maintained by the research sponsor with reasonable care being taken by the Investigators and facility to prevent damage to, or unauthorized use of the equipment.

## 10.9 Training Requirements

PI and all study personnel are well familiar with the procedure and device operation including all related tools and equipment. No training or additional instructions are required prior to study initiation.

## 10.10 Modification of Protocol

The protocol may be amended with the agreement of the sponsor and upon notification of and approval by the IRB / EC.

Investigators should review the contents of this protocol. Subsequent alterations should only be made in writing in conjunction with the sponsor.

Medically significant amendments to the protocol (e.g., changes that increase the risk or the inconveniences for the patient, inclusion of new categories of patients, significant modifications to the study device, etc.) must be approved by the local IRB / EC prior to implementation and authorized representative, as applicable.

## 10.11 Data Retention/Archiving Data

The Investigator must keep the following documents in a secure place for at least 2 years after the last clearance of a marketing application or at least 2 years have elapsed since the formal discontinuation of clinical development of the investigational product.

- A signed copy of the final protocol and amendments.
- Copies of the subjects' evaluation forms, data clarification forms and any associated subject-related raw data or where applicable, authorized copies of raw data.
- The subjects' signed Informed Consent forms.

## 10.12 Site Monitoring

The study monitors are designated as agents of Lumenis and are assigned to oversee the conduct and progress of the study and to be the principal communication link between Lumenis and investigator.

The study monitors will be involved in monitoring of sites and records, to ensure continued compliance with the protocol and adequacy of the investigator and the facility to carry out the study.

**DOC No.: 1005715**

Revision: B

State: Released

ECO No: GEN-0007426

Effective Date: 02-Jun-2016

**Description: Surgical. Protocol LUM-SBU-VP-15-02, Ablation efficacy of contact side firing fiber in predefined settings for treating BPH**

The study will be monitored by representatives of Lumenis Medical, Ltd. by telephone, in writing and during on-site visits. At a minimum, site visits will be scheduled prior to the initiation of the study, and at the end of the study. The purpose of site visits will be to ensure compliance with the investigational plan, to ensure appropriate use of investigational devices, and to inspect and retrieve study data.

### **10.13 Termination of Study**

Lumenis reserves the right to discontinue the study at any time for administrative or other reasons. Written notice of study termination will be submitted to the investigator in advance of such termination. Termination of a specific site can occur because of (but is not limited to) inadequate data collection, low subject enrollment rate, achievement of the total enrollment, or non-compliance with the protocol or other clinical research requirements

### **10.14 Reporting Requirements**

The investigator must promptly report to Lumenis any withdrawal of IRB / EC approval at the site. Additional reporting requirements include:

- Notify Lumenis' designee and the IRB / EC of any severe adverse device effect, whether anticipated or unanticipated, that occurs during the study as soon as possible, but in no event later than 10 working days after the investigator first learns of the effect. This report is to include a description of the effect, subsequent treatments, clinical outcomes, and outcome diagnoses. If the site personnel are not sure whether an event meets these criteria, they should call the clinical monitor.
- Notify Lumenis or Lumenis's designee and the IRB / EC immediately (within 24 hours) if an emergency situation arises in which the subsequent treatment, in the best interests of the subject, resulted in a deviation from the protocol. This should be followed with written confirmation that describes the emergency action and outcomes, to Lumenis and the IRB / EC within 5 working days.
- Report to the IRB / EC and Lumenis, within 5 working days, the use of the study device without signed informed consent from the subject.
- Report adverse events in accordance with 21 CFR 803.
- Submit regular progress reports to the IRB / EC and Lumenis or Lumenis' designee, as requested by the investigators or IRB/ EC.
- Submitting a final report on the study to the IRB / EC and Lumenis or Lumenis's designee within 3 months after termination or completion of the study.

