#### **9.1.2 Adverse Device Effect**

Adverse event related to the use of an investigational medical device. Adverse Device Effect can be an anticipated serious adverse Device Effect which by its nature, incidence, severity or outcome has been identified in the risk analysis report or unanticipated if it has not been identified in the risk analysis report.

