#### **9.1.3 Serious Adverse Events**

NOTE: The term serious is not synonymous with severity, which may be used to describe the intensity of an event experienced by the subject. An AE that does not meet any of the below criteria will be classified as non-serious.

A serious adverse event is any event that:

4. led to death,
5. led to serious deterioration in the health of the subject, that either resulted in:
  - 5.1. a life-threatening illness or injury, or
  - 5.2. a permanent impairment of a body structure or a body function, or
  - 5.3. in-patient or prolonged hospitalization, or
  - 5.4. medical or surgical intervention to prevent life-threatening illness or injury or permanent impairment to a body structure or a body function,
6. led to foetal distress, foetal death or a congenital abnormality or birth defect

Any adverse events or complications reported by the patient or observed by the physician that occur during or after treatment with the device will be recorded in the medical record or source document and on the dedicated Case Report Form. The investigator will determine if the AEs are device related or procedure related. This assessment shall include the onset date, resolution date, severity, seriousness, frequency, additional treatment required and outcome.

Each adverse event should be assessed according to the following criteria:

**Description: Surgical. Protocol LUM-SBU-VP-15-02, Ablation efficacy of contact side firing fiber in predefined settings for treating BPH**

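### Section 10.14 makes the one unconditional in-study harm notice to the IRB/EC depend on *severe* rather than *serious*, so a serious device effect not graded severe has no assured event-level route there before the final report

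*Combined protocol and SAP*

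**What the plan says.** Section 10.14 (Reporting Requirements) tells the investigator to notify the sponsor's designee "and the IRB / EC of any severe adverse device effect, whether anticipated or unanticipated, that occurs during the study as soon as possible". The outer limit is 10 working days from first knowledge. The same bullet tells site staff who are unsure whether an event qualifies to call the clinical monitor.

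The definitions come earlier. Section 9.1.3 states: "The term serious is not synonymous with severity, which may be used to describe the intensity of an event experienced by the subject". It then defines a serious event by outcome: death, serious deterioration in health with one of four listed results, or foetal harm. Section 9.1.4.1 grades severity as mild, moderate or severe, and describes severe as a matter of intensity.

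On device effects, 9.1.2 uses the other word: "Adverse Device Effect can be an anticipated serious adverse Device Effect which by its nature, incidence, severity or outcome has been identified". The body of 9.2.1 also speaks of serious events and serious device effects, and section 12 expands SAE with *Serious*. The heading of 9.2.1, however, expands SAE with *Severe*.

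**The concern.** By the protocol's own definitions, the trigger in 10.14 is an intensity grade, whereas the rest of the safety section is built on seriousness. The 10.14 notice is the only one prompted by a harm during the study that goes to the IRB/EC without depending on an outside rule, a judgement, a protocol deviation or a request. If its trigger is the wrong word, a serious device effect graded moderate falls outside it.

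What is at stake is oversight while subjects are still being treated. Safety is part of the primary objective (4.1), and 10.14 is the text a site would follow when deciding what to send to the IRB/EC. No estimate or summary is at risk: 8.1 lists all reported adverse events whichever word 10.14 uses.

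**Working it through.** There is no figure in the plan to reproduce. The check sets the definitions side by side and then traces one kind of event through every reporting route.

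**Step 1: do the two categories differ?**
- Serious (9.1.3): for events other than death or foetal harm, item 5 first requires a serious deterioration in health. That deterioration must then have resulted in a life-threatening condition, permanent impairment, hospitalization (in-patient or prolonged), or an intervention to prevent a life-threatening condition or permanent impairment.
- Severe (9.1.4.1): significant discomfort and/or interference with activity, need for intervention or treatment, and sequelae. The text does not say whether every element must be present.
- Moderate (9.1.4.1): may interfere with usual activity and need further intervention or treatment, with sequelae possible.

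Need for intervention therefore appears under both moderate and severe, and neither grade refers to the outcomes that define serious. A device effect with serious deterioration that needs a preventive intervention and then resolves could be graded moderate or severe. The categories overlap, but neither contains the other.

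**Step 2: where does a serious device effect not graded severe go?**

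| Route | Condition | Assured to reach IRB/EC during the study? |
|---|---|---|
| 9.2.1, all serious events to the sponsor's monitor, 24 hours | none | No; recipient is the sponsor |
| 9.2.1, serious events to the EC | national regulations or the EC require it | No |
| 9.2.1, anticipated events to the IRB/EC | sponsor or investigator thinks subject safety or study conduct is likely to be affected | No |
| 10.14, device effect, 10 working days | must be *severe* | No, as worded |
| 10.14, emergency notice, 24 hours | only "if an emergency situation arises in which the subsequent treatment, in the best interests of the subject, resulted in a deviation from the protocol" | No |
| 10.14, progress reports | "as requested by the investigators or IRB/ EC" | No |
| 10.14, final report | none; due "within 3 months after termination or completion of the study" | No; comes after the study |

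Two other provisions do not fill the gap. One line reads "Report adverse events in accordance with 21 CFR 803", and names neither a recipient nor a deadline. The interim report in 8.2 names no IRB/EC recipient.

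Count of in-study routes to the IRB/EC for a harm: two in 9.2.1 plus three in 10.14 = 5. Four depend on regulation, opinion, deviation or request; the fifth depends on *severe*.

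**Step 3: timing at the outer limit.** Assumptions: 3 months = 13 weeks, surgery on the day of enrolment, completion at the last subject's 3-month visit, and an event at surgery. Enrolment takes 12 to 16 weeks (7.1).
- 10.14 applies: 10 working days = 2 weeks.
- 10.14 does not apply and every other route fails, last subject: 13 + 13 = 26 weeks to the final-report deadline.
- Same, first subject: 12 + 13 + 13 = 38 weeks to 16 + 13 + 13 = 42 weeks.

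These are upper limits, not expected delays. In this scenario all subjects have been treated before the final report is due.

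**The case against.** The strongest reply is that the wording differs but little follows from it. Several parts of that reply stand.

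- A reader might infer that any capsule perforation that lengthens the hospital stay is a serious event that escapes notice. The documents do not support this. Longer hospitalization counts under 9.1.3 only where the event led to serious deterioration in health.
- A reader might infer that an event without sequelae cannot be severe. Section 9.1.4.1 does not clearly make sequelae necessary, so many serious events could be graded severe and fall under 10.14.
- Perforation and bleeding are the anticipated device risks in 9.3.2. The anticipated-event route in 9.2.1 therefore applies to them, and the opinion of either the sponsor or the investigator is enough to trigger it.
- The call-the-monitor instruction is in the 10.14 bullet itself, and the monitor already receives every serious event within 24 hours.
- Section 10.2 commits the study to the Medical Device Directive, ICH GCP and local law. If any of these, or the EC, requires reports of serious events, there is no gap in practice. It therefore goes too far to say that a site could properly withhold such an event.
- A reader might infer that the IRB/EC would never learn of it. The final report is unconditional and, under 8.2, covers adverse events.

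None of this supplies an unconditional event-level notice during the study. Section 10.2 does not say whether any rule requires reports of serious events to the EC. A site that has graded an event moderate may not regard itself as unsure.

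**Conclusion.** The point holds as a wording defect with a narrow practical consequence. As written, a device effect that is serious under 9.1.3, including the serious-deterioration condition where item 5 applies, but is not graded severe has no unconditional event-level route to the IRB/EC before the final report. Four of the five in-study routes are conditional and the fifth uses the wrong trigger.

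This conclusion rests on a literal reading of 10.14. The word is probably a slip, since the 9.2.1 heading makes the same substitution above text about serious events. Nothing in the documents shows that the sponsor meant to narrow reporting.

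The frequency of such events cannot be estimated. The documents give no rate for serious, non-severe device effects, and 9.3.2 describes complications with holmium ablation as rare without giving a figure. A probability of seeing one among the 20 subjects would only reflect whatever rate was assumed. Whether any practical gap exists also depends on what national rules and this IRB/EC require, which the protocol does not state. The descriptive results are not affected. The change is worth making because it is small, not because harm has been shown.

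**What to change.** In 10.14, change *severe adverse device effect* to *serious adverse device effect*. Writing *serious or severe* instead would also keep the present coverage of severe, non-serious effects. In the 9.2.1 heading, replace *Severe* with *Serious* so that it matches 9.1.3 and section 12.

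This takes a short amendment with IRB/EC approval under 10.10. It needs no extra subjects, visits or analyses. The downside is possibly a few extra notices to the IRB/EC; if each subject had at most one such event, the number could not exceed 20.
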